Study Protocol

Personalized Booster Feedback After Alcohol Health Education

NCT03440476

6/23/2022

Principal Investigator:

[name].

Description and Purpose of the Project

Heavy episodic alcohol use within the college student population is widespread, creating problems for student drinkers, their peers, and their institutions. Negative consequences from heavy alcohol use can be mild (e.g., hangovers, missed classes), to severe (e.g., assault, even death). Although online interventions targeting college student drinking reduce alcohol consumption and associated problems, they are not as effective as in-person interventions. Online interventions are cost-effective, offer privacy, reduce stigma, and may reach individuals who would otherwise not receive treatment. In a recently completed randomized, controlled trial, an emailed booster with personalized feedback improved the efficacy of a popular online intervention (Braitman & Henson, 2016). Although promising, the booster incorporated in the study needs further empirical refinement.

The current project seeks to build on past progress by further developing and refining the booster. In particular, one aspect missing from online interventions is a connection with a person invested in improving the student's outcomes. The current study aims to generate a personal connection for online interventions through a follow-up booster emailed by a member of the research staff. Outcomes will be compared for participants who receive a follow-up booster with similar content, but is clearly automatically generated and not from any particular individual.

There are 3 conditions: all participants receive the initial online intervention targeting college drinking. Condition 1 (the control group) receives an email with a reminder to complete the follow-up surveys, but no feedback (i.e., no booster). Condition 2 receives an emailed booster with normative feedback plus protective strategies feedback, clearly automatically generated. Condition 3 receives an emailed booster with normative feedback plus protective strategies feedback, from a member of the research staff. The booster content alone (automatically generated) may be efficacious, or the additional personal connection may enhance the effect.

Primary Aims

The aim of the current study is to examine if personal contact enhances the tailored feedback received via booster email.

Participants

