Baseline: Upon arrival at the research lab, participants are provided with the informed consent document, and have the opportunity to ask questions. After consenting to participate, they are directed to one of the computers in the lab. Because data are collected in a computer lab setting, each computer has a privacy partition (behind and beside the monitor). This is to minimize the possibility of participants viewing each other's screens. Additionally, participants are provided with headphones to minimize disruption from the other computers. All participants complete a computerized survey at the beginning of their first appointment that assesses alcohol use, alcohol-related problems, protective behavioral strategies for drinking and their perceived effectiveness, motives and expectancies for alcohol use, anonymized social network characteristics, context of their most recent drinking occasion, marijuana and tobacco use, and demographics measures. Upon beginning the survey, participants are randomly assigned within the survey system to one of the three study conditions: neutral email (no feedback), auto-generated booster email (feedback, no warmth), warm booster email (feedback written by a person using warm, personable language). After completing the initial assessment, participants are then directed to navigate through the *eCHECKUP TO GO for Alcohol* program (San Diego State University Research Foundation, 2018) until it is completed (approximately 20-30 minutes).

Follow up assessments: Approximately one and three months after the initial assessment, researchers send each participant an email reminding them to complete the follow-up assessment in exchange for payment. This email includes a link to an online follow-up survey that assesses alcohol use, related problems, protective behavioral strategies for drinking and their perceived effectiveness, anonymized social network characteristics, context of their most recent drinking occasion, and marijuana and tobacco use.

Boosters: Approximately two weeks after the intervention, all participants receive an additional email from the researcher. Information in the emails for the experimental booster groups serve as a booster to the original intervention. Baseline data are used to provide students with normative information (e.g., typical drinking among ODU students who are male/female

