depending on the gender of the recipient), and reminders of protective behavioral strategies they can use to reduce drinking-related harm. In the auto-generated booster email condition, the feedback is delivered neutrally: “Hello, This feedback has been automatically generated for Carlton based on your answers to the online survey you completed in the research lab for the Project ‘Personalized Booster Feedback after Alcohol Health Education’”), whereas in the warm booster email condition, the feedback is delivered by a person using warm, personable language (i.e., Dear Carlton, My name is [name] and I’m your personal research coordinator for the Project ‘Personalized Booster Feedback after Alcohol Health Education’. I track your responses over the course of the study, and I’m writing to give you feedback about your answers to the online survey you completed in the research lab”). Participants in the control condition receive an email with no feedback.

Measures

The same measures are included in baseline and the follow-up surveys:

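### Does the warm email's bundle of sender, tone and tracking statement undermine the test of personal contact?

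*Protocol*

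**What the plan says.** Under Primary Aims, the protocol sets out to "examine if personal contact enhances the tailored feedback received via booster email". The Description and Purpose section presents the comparator as similar content that is "clearly automatically generated and not from any particular individual", and states that "Condition 3 receives an emailed booster with normative feedback plus protective strategies feedback, from a member of the research staff".

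Study Procedure (Baseline) labels the two arms "auto-generated booster email (feedback, no warmth), warm booster email (feedback written by a person using warm, personable language".

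Study Procedure (Boosters) says that about two weeks after the intervention "all participants receive an additional email from the researcher". It then quotes the two openings. The automatic one begins, after a greeting, "This feedback has been automatically generated for" the recipient. In the warm arm "the feedback is delivered by a person using warm, personable language": the writer gives a name, claims the role of the student's own research coordinator, and adds "I track your responses over the course of the study".

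Under Measures, alcohol use comes from a modified Daily Drinking Questionnaire covering the past 30 days. Alcohol-related problems and protective strategies are also questionnaire measures. No primary outcome is singled out.

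**The concern.** Three features of the text invite the worry.

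- **The factor seems to shift.** The Description and Purpose section contrasts the arms by who sends the email. The Baseline text adds tone. The sample wording adds a personal coordinator who follows the student's answers. There is one warm-versus-automatic contrast and at least three elements, so their separate effects cannot be identified. The same result might be written up as an effect of the sender or as an effect of warmth.
- **The sender is described two ways.** If the automatic email visibly came from the researcher, the sender element would be only partly varied, and a null result would say less about personal contact.
- **The outcomes are self-reported after the email.** Students told that someone follows their responses might answer differently without drinking differently. At the 1-month survey roughly the first half of the 30-day recall window predates the booster. A true change in drinking could affect only the later part of that window, while a change in reporting could affect the whole answer.

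If these points held in full, the contrast that carries the stated aim would be hard to interpret.

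**Working it through.** **Step 1. Do the descriptions of the contrast conflict?**

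| Place in Protocol | Warm arm | Automatic arm |
|---|---|---|
| Description and Purpose | from research staff; meant to create a personal connection | visibly automatic, no individual |
| Study Procedure, Baseline | written by a person, warm language | auto-generated, no warmth |
| Study Procedure, Boosters | delivered by a person, warm language; sample opening with coordinator and tracking | neutral delivery; sample opening says it is automatic |

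The Baseline and Boosters texts agree almost word for word that the warm email is by a person and in warm language, so neither defines the contrast by tone alone. The Description and Purpose section is not confined to sender either. It says that online programs lack a connection with someone who cares how the student fares, and that the study aims to supply one. A named coordinator who writes warmly and follows the student's answers is a natural way to do that. The table shows a summary followed by operational detail, not three rival definitions.

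**Step 2. Is the sender contradictory?** The statement "all participants receive an additional email from the researcher" covers all three arms, control included, so its likely meaning is that the study team dispatches the email. How the automatic email is presented is stated elsewhere: "clearly automatically generated and not from any particular individual" in the Description and Purpose section, and "This feedback has been automatically generated for" in its opening. The displayed sender and sign-off are not given for any condition, but the protocol quotes only openings.

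**Step 3. How large could a reporting artefact be?** The only figures available are N = 180 and 76% retention (Participants section). Equal allocation, two-sided 0.05, an unadjusted comparison and a normal approximation are assumptions.

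- Completers per arm: 180/3 × 0.76 = 45.6.
- Scaling factor: k = √(45.6/2) = 4.775.
- Chance of a false result favouring warm, when reported drinking shifts down by s SD and true drinking does not change: 1 − Φ(1.960 − s·k).

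| Assumed shift s (SD) | 45.6 per arm | 60 per arm (k = √(60/2) = 5.477) |
|---|---|---|
| 0 | 2.5% | 2.5% |
| 0.1 | 6.9% | 7.9% |
| 0.2 | 15.7% | 19.4% |
| 0.3 | 29.9% | 37.6% |

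The shift that doubles 2.5% to 5% is (1.960 − 1.645)/4.775 = 0.066 SD, or 0.058 SD with 60 per arm.

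The arithmetic is sound, but every value of s is chosen, not found in the protocol. A shift toward more candour in the warm arm would act the other way.

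**Step 4. Is the tracking statement a clear difference in what students know?** Only in part. Every participant gives name, email and phone number (Recruitment Procedure) and is sent follow-up reminders that offer payment (Study Procedure). The automatic opening also tells the student that the feedback rests on the survey answered in the lab. Students in all arms can see that their answers are linked to them. The warm opening makes this personal and continuing, which is a difference of degree.

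**Step 5. Does naming the contrast a package change any number?** No. The stated power of .813 comes from a simulation whose model and covariances are not given, so a closed formula can neither confirm nor refute it. The point does not depend on it: N, allocation and the comparison stay the same whatever the contrast is called.

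**The case for a change.** The strongest case for acting is that arm definitions belong in the protocol and cannot be left to an analysis plan. The warm sample text is introduced as what the condition is, not as a loose example. The sender is the element by which the Description and Purpose section separates the arms, yet no place states what the participant sees as sender. The remedy would also cost only wording and could be applied even after data collection.

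Part of this stands. The two sender phrases do not match literally, and a line giving the displayed sender and sign-off in each condition would settle the matter. It is also true that the quoted warm opening alone speaks of tracking, that the effects of the elements cannot be separated, and that differential reporting is possible.

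The rest does not carry. Non-identifiability of the separate elements would be a fault only if the protocol claimed to isolate one of them, and it does not. Differential reporting is a general caveat for a self-report trial of visibly different emails, with neither size nor direction available here. Rewriting the aim around self-reported drinking would go beyond tidying: with no primary outcome named, it would narrow the aim to one of several measures, possibly after data had been collected.

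**Conclusion.** No change to the plan follows. The warm-versus-automatic comparison is randomized and valid for what it compares: a booster presented as a warm message from a personal coordinator against similar feedback presented as automatic. The bundle appears to be the intended form of the personal connection under study. A sensible analyst would describe any difference as an effect of that whole package on self-reported outcomes.

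What survives is clerical. The phrase about no particular individual and the phrase about the researcher should be read together, most plausibly with the second meaning dispatch by the study team. Stating the displayed sender in each condition would remove the doubt without altering an arm, the sample size, an analysis or a result.

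This conclusion assumes that the full automatic email is presented as automatic, as its opening and the Description and Purpose section indicate. If it carried a visible personal sender, the contrast would be weaker than intended, though still valid for the emails actually sent. The effect of any reporting shift cannot be quantified from the protocol. The range of 6.9% to 29.9% for assumed shifts of 0.1 to 0.3 SD shows only the sensitivity of a comparison of this size.

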Participants’ **alcohol use** is assessed using a modified version of the Daily Drinking Questionnaire for the past 30 days (Collins et al., 1985). Additionally, participants describe specific aspects regarding their drinking in the past 30 days (e.g., highest consumption in a single day). **Descriptive Norms** are assessed by modifying the DDQ to reflect their expectations for typical male students at the same institution, typical female students at the same institution, and close friends. Injunctive Norms are assessed using 10 items (Carey et al., 2010). **Alcohol-related problems** are assessed using the 48-item Young Adult Alcohol Consequences Questionnaire (YAAQ; Read et al., 2006), modified to assess the past 30 days rather than the past year. **Protective behavioral strategy** (PBS) use is assessed using Sugarman and Carey’s (2007) Strategy Questionnaire (SQ). **Perceived effectiveness of PBS** is assessed by modifying the instructions and response scale for Sugarman and Carey’s (2007) measure to assess how effective participants perceive each strategy to be. **Importance of PBS** use for all people and self are assessed with 10 items created by the researcher. **Alcohol expectancies** are assessed using the Comprehensive Effects of Alcohol questionnaire (CEOA; Fromme et al., 1993). **Motives for alcohol use** are assessed using the Drinking Motives Questionnaire (DMQ; Cooper, 1994). **Alcohol beliefs** about how salient alcohol use is to college life are assessed using the College Life Alcohol Salience Scale (CLASS; Osberg et al., 2010). **Social network** and affiliated characteristics are assessed using the adapted version (DeMartini et al., 2013) of the Brief Important People Interview (BIP; Zywiak et al., 2002). Participants are asked to report characteristics and context for their **most recent drinking occasion**. This assessment is a collection of items mostly created by the researcher, but incorporates a modified version of the **Alcohol Offers** scale (Read et al., 2005), and a truncated, occasion-specific version of **drinking motives** (Cooper, 1994). **Marijuana use** is assessed similar to prior research (e.g., Collins et al., 2014), and **tobacco use** is assessed using items created by the researcher. **Demographics and general information** are collected during the initial assessment only; participants report their age, race, sex, Greek affiliation (i.e., membership in fraternities or sororities), GPA, class standing, athletic status student status (full- versus part-time), residential status, relationship status, sexual identity, height, and weight (for blood alcohol content calculations).

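### Do the protocol's survey lists leave norms, motives and expectancies unmeasured at follow-up?

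*Protocol*

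**What the plan says.** Two parts of the protocol describe what the surveys contain.

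- **Measures.** The section opens with "The same measures are included in baseline and the follow-up surveys" and then describes the instruments. Descriptive norms "are assessed by modifying the DDQ to reflect their expectations for typical male students at the same institution", and for typical female students and close friends. Injunctive norms, the expectancies questionnaire (CEOA), the motives questionnaire (DMQ), the alcohol-salience scale (CLASS) and importance of protective strategies appear in the same list. The one exemption is demographics and general information, which "are collected during the initial assessment only".
- **Study Procedure, baseline paragraph.** The baseline survey "assesses alcohol use, alcohol-related problems, protective behavioral strategies for drinking and their perceived effectiveness, motives and expectancies for alcohol use". The list then runs through social network, drinking context, marijuana and tobacco to demographics.
- **Study Procedure, follow-up paragraph.** Participants are sent a link to a survey on "alcohol use, related problems, protective behavioral strategies for drinking and their perceived effectiveness, anonymized social network characteristics, context of their most recent drinking occasion". Tobacco and marijuana close the list. Motives, expectancies and demographics are not named.

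Neither Study Procedure paragraph names norms, alcohol salience or importance of protective strategies. The Description section says both booster conditions receive normative feedback together with feedback on protective strategies.

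**The concern.** The two Study Procedure lists run in the same order, and the second lacks motives and expectancies in the middle. That looks like a deliberate baseline-only choice, which the opening sentence of Measures rules out. Demographics are also dropped, but Measures explains that omission and does not explain the other two.

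Norms look more serious. The booster has two components, normative feedback and protective-strategy reminders. A follow-up form built literally from Study Procedure would measure the strategy component and not the normative one. The trial could then test whether a booster changed strategy use but not whether it changed perceived norms, and a positive or null result would be harder to explain. Survey items that were never asked cannot be recovered later. With 76% retention of 180 students, as the Participants section assumes, the gap would affect about 180 × 0.76 = 136.8, or 137, students at both follow-ups.

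**Working it through.** No power or sample-size figure depends on this point, so the check is a comparison of three lists: Measures, the baseline paragraph and the follow-up paragraph.

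| Construct | Measures | Baseline paragraph | Follow-up paragraph |
|---|---|---|---|
| Alcohol use | every wave | named | named |
| Alcohol problems | every wave | named | named |
| Protective strategy use | every wave | named | named |
| Perceived effectiveness of strategies | every wave | named | named |
| Social network | every wave | named | named |
| Most recent drinking occasion | every wave | named | named |
| Marijuana | every wave | named | named |
| Tobacco | every wave | named | named |
| Motives (full DMQ) | every wave | named | not named |
| Expectancies (CEOA) | every wave | named | not named |
| Demographics | baseline only | named | not named |
| Descriptive norms | every wave | not named | not named |
| Injunctive norms | every wave | not named | not named |
| Alcohol salience (CLASS) | every wave | not named | not named |
| Importance of strategies | every wave | not named | not named |

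Measures holds 15 constructs. The baseline paragraph names 15 − 4 = 11, and the follow-up paragraph names 11 − 3 = 8.

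**Norms.** Four constructs are missing from both paragraphs. If the paragraphs were exhaustive, norms, alcohol salience and importance of strategies would not be collected even at baseline, although Measures describes an instrument for each. The sensible reading is that the paragraphs abbreviate. Since norms are absent from the baseline paragraph too, their absence from the follow-up paragraph is no sign that they were dropped after baseline. Measures alone addresses their timing, and it includes follow-up.

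**Motives and expectancies.** Of the three constructs named at baseline but not at follow-up, demographics agree with Measures. The other two, DMQ and CEOA, do not sit well with it, and here the text is ambiguous. The follow-up paragraph does not say that it covers only the domains it names, so a form with every Measures item except demographics satisfies both sections.

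**Motives on the narrow reading.** Measures places a shortened, occasion-specific motives scale inside the most-recent-occasion items, and the follow-up paragraph keeps those items. Even if that paragraph governed, motives would not be wholly absent at follow-up; only the full DMQ would be.

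**The figure of 137.** This is the expected number retained, not the size of a loss. It becomes a loss only if the paragraphs are exhaustive and override Measures.

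**The case for a change.** The strongest opposing case is that the schedule of assessments belongs in the protocol and is not normally left to an analysis plan. Abbreviation explains a construct missing from both paragraphs, but it explains poorly why a parallel list keeps perceived effectiveness, social network and tobacco and loses two items from its middle. A reader also needs to know which section governs to judge whether later analyses of motives or expectancies were planned.

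Part of this stands. The mismatch over the full DMQ and CEOA is real, and nothing in the protocol explains it. It does not carry over to norms. Nor does it reach the trial's question: Primary Aims gives one aim, whether personal contact enhances the tailored feedback, and states no aim on mediation or change in norms. Motives and expectancies are not described as booster content. Both booster arms receive normative feedback and differ in personal delivery, so norms data would bear more directly on booster versus control than on the contrast the aim describes.

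**Conclusion.** The concern does not call for a change. The norms part fails, because the only text on their timing puts them at baseline and at both follow-ups. What is left is a clerical inconsistency about whether two questionnaires, the full DMQ and the CEOA, are repeated at 1 and 3 months. Both are named for baseline in either section, and following Measures collects both at follow-up as well. A sentence or a measure-by-wave table would tidy the wording, but the stated aim, the drinking outcomes, the sample of 180 and the power of .813 would all stay as they are.

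This rests on two assumptions: that Measures, which describes each instrument and states its own exception, governs over a narrative summary; and that the follow-up form was built accordingly. The form itself is not in the protocol. If it left out the DMQ and CEOA, the loss would be follow-up data on two secondary questionnaires, with occasion-specific motives still collected.
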